### 4.3. Analytic Methods

#### 4.3.1. Descriptive Analysis

Descriptive statistics are typically generated for all study variables. The descriptive statistics include means, standard deviations, 1st quartiles, medians, 3rd quartiles, interquartile ranges, and minimum and maximum values for continuous variables (eg, age at diagnosis) and frequencies and percentages for categorical variables (eg, race, performance status).

No statistical comparisons will be performed. CCI [REDACTED]

#### 4.3.2. Time to Event Analysis

Single time to event analyses will be conducted as specified under the study objectives. CCI [REDACTED]

Real-world time to event outcomes in this study will include:

- rwEFS/rwRFS for the first 3 R/R-based lines of therapy. rwEFS will be defined as the time from the treatment initiation date (for the first agent in the first regimen in the first line of Mylotarg-containing therapy) to the date of treatment failure (TF), relapse from Complete Response (CR) or better, or death from any cause, whichever comes first. TF is defined as failure to achieve CR or better following up to 3 cycles of Mylotarg. rwRFS will be defined as the time from the treatment initiation date (for the first agent in the first regimen in the first line of therapy) to the date of a relapse event, or death from any cause, whichever comes first.
- rwOS, from the first line of therapy through the end of record or death, whichever occurs first, and
- Duration of therapy across lines of therapy from the first line of therapy through the third R/R-based line of therapy.

The time origin for analysis of rwEFS/rwRFS is the start of therapy within each specific line of therapy, and the terminal event is the earlier of an R/R event or death. The time origin for analysis of rwOS is the start of therapy within the first line of therapy, and the terminal event is death. Patients who are not indicated to be deceased at last known contact (patients who are alive, or lost to follow-up) will be censored. The time origin for analysis of duration of therapy is start of Mylotarg, and the terminal event is discontinuation of that therapy.

#### 4.3.3. Methods under Objective 1

*Objective 1: To describe the demographic and clinical characteristics as outlined in the variable list below for patients diagnosed with AML who received Mylotarg in a real-world setting.*

Descriptive analysis as detailed in [Section 4.3.1](#) will be conducted for work under this objective. Demographic characteristics that will be reported will include sex, patient age, race/ethnicity, height, weight, BMI, insurance status, and region of residence closest to the index date. Clinical characteristics that will be reported will include comorbidities and comorbidity index score, ECOG score, and disease characteristics, such as stage at index date, cytogenetic testing at index date, and whether the AML diagnosis was de novo versus secondary.

Demographic and clinical characteristics will not be stratified by a primary grouping variable.

#### 4.3.4. Methods under Objective 2

*Objective 2: To describe the treatment patterns from the diagnosis of AML through the end of the third R/R-based line of therapy.*

Analysis under this objective will include all study patients. Descriptive analysis as detailed in [Section 4.3.1](#) will be conducted for work under this objective. Treatment patterns include description of regimens within line of therapy for the first 3 R/R-based lines of systemic therapy as well as the description of sequences of regimens across the first 3 R/R-based lines of systemic therapy. Description of treatment regimens within line includes the frequency and percentage of each agent/regimen received, by regimen in sequence, by line, for the first 3 R/R-based lines of systemic therapy. In addition, the analysis will descriptively characterize the starting dose and dose changes of Mylotarg in each of the first lines of therapy.

Duration of treatment will also be descriptively analyzed across lines of therapy, starting with the first agent or regimen in the first line of therapy for the first 3 R/R-based lines of therapy.

### 4.3.5. Methods under Objective 3

*Objective 3: To describe the effectiveness outcomes of treatment of AML patients who received Mylotarg in a real-world setting*

Analysis under this objective will include all study patients. The outcomes of interest under this objective are rwEFS/rwRFS and rwOS. Time to event analysis as described in [Section 4.3.2](#) will be utilized.

The Kaplan-Meier product limit estimator will be employed to evaluate rwEFS/rwRFS and rwOS. The time origin for these analyses will be the start of the treatment in the respective line of therapy for rwEFS/rwRFS for the first 3 R/R-based lines of therapy. The time origin of rwOS analysis is the start of the earliest line of Mylotarg therapy. rwEFS/rwRFS and rwOS analyses for lines of therapy will be limited to patients who received treatment during the line of interest.

rwEFS will be defined as the time from the treatment initiation date (for the first line of Mylotarg-containing therapy) to the date of treatment failure (TF), relapse from CR or better, or death from any cause, whichever comes first. TF is defined as failure to achieve CR or better following up to 3 cycles of Mylotarg. Accordingly, the time origin for rwEFS will be the start of Mylotarg in the first line of therapy in which it is used. The terminal event for analysis of rwEFS is the earlier of treatment failure, relapse from CR or better (as evidenced by provider documentation), or death. Patients who have not died or experienced an event by the date of last contact within the medical record will be censored for analysis of rwEFS.

rwRFS will be defined as the time from the treatment initiation date (during the first line of Mylotarg-containing therapy) to the date of a relapse event, or death from any cause, whichever comes first. The time origin for rwRFS will be the start of Mylotarg in the first line of therapy in which it is used. The terminal event for analysis of rwRFS will be the earlier of a relapse event (as evidenced by provider documentation), or death. Patients who have not died or experienced a relapse event by the date of last contact within the medical record will be censored for analysis of rwRFS.

The time origin of rwOS analysis is the start of the first Mylotarg use. The terminal event for analysis of rwOS is date of death. Note that Social Security Disability Insurance (SSDI) records have an expected lag of up to 4 months. Accordingly, patients who are not indicated to be deceased in clinical records or SSDI records will be censored for rwOS analysis as of the later of 1) the latest date known alive within the clinical record, 2) 4 months prior to the date of most recent SSDI update.

Separate Kaplan-Meier analyses will be conducted for each rwEFS, rwRFS and rwOS endpoint.

#### 4.3.6. Methods under Objective 4

*Objective 4: To evaluate response among AML patients who received Mylotarg in a real-world setting.*

- a. First and best response for each regimen in the first qualifying Mylotarg-containing R/R-based line of therapy.
- b. Time to best response for each regimen in the first qualifying Mylotarg-containing R/R-based line of therapy.
- c. Duration of best response for each regimen in the first qualifying Mylotarg-containing R/R-based line of therapy.

Response will be assessed for the first and best overall response to treatment for each regimen in the first qualifying Mylotarg-containing R/R-based line of therapy during the study period. Response classifications will be made based on the treating physician's documentation of response itself, typically informed by radiological scan reports noted in the patient record. Classification is made to the following categories: complete response (CR), partial response (PR), stable disease (SD), progressive disease (PD), and not evaluable (NE), each based on the treating physician's statements. In cases where complete response with partial hematologic recovery (CRh), complete response with incomplete hematologic recovery (CRi), and morphologic leukemia-free state (MLFS) are explicitly included in the treating physician's statements, these additional classifications will be documented. The date of the best overall response for each regimen in the first qualifying Mylotarg-containing R/R-based line of therapy will be collected. Responses captured are based on treating physician's assessment in the medical record. Overall response rate will be defined as a percentage of patients whose best response is either CR, CRi, or MLFS, where available. Time to best response and duration of best response will be assessed using the descriptive techniques described above.

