### 9.7.2. Time to Event Analysis

Single time to event analyses will be conducted as specified under the study objectives.

CCI

Real world time to event outcomes in this study will include:

- rwEFS/rwRFS for each of the first three R/R-based lines of therapy. rwEFS will be defined as the time from the treatment initiation date (for the first line of therapy) to the date of treatment failure (TF), relapse from Complete Response (CR) or better, or death from any cause, whichever comes first. TF is defined as failure to achieve CR or better following up to 6 cycles of Mylotarg. rwRFS will be defined as the time from the treatment initiation date (for the first line of therapy) to the date of a relapse event, or death from any cause, whichever comes first.
- rwOS, from the first line of therapy through the end of record or death, whichever occurs first, and
- Duration of therapy across lines of therapy from the first line of therapy through the third R/R-based line of therapy.

The time origin for analysis of rwEFS/rwRFS is the start of therapy within each specific line of therapy, and the terminal event is the earlier of an R/R event or death. The time origin for analysis of rwOS is the start of therapy within the first line of therapy, and the terminal event is death. The time origin for analysis of duration of therapy is start of Mylotarg, and the terminal event is discontinuation of that therapy.

### 9.7.3. Methods Under Objective 1

*Objective 1: To describe the demographic and clinical characteristics as outlined in the variable list below for patients diagnosed with AML who received Mylotarg in a real-world setting.*

Descriptive analysis as detailed in [Section 9.7.1](#) will be conducted for work under this objective. Demographic characteristics that will be reported will include the distribution of sex, patient age, race/ethnicity, height, weight, BMI, insurance status, and region of residence closest to the index date. Clinical characteristics that will be reported will include the distribution of comorbidity status and comorbidity index score, ECOG score, and disease characteristics, such as stage at index date, cytogenetic testing at index date, and whether the AML diagnosis was de novo versus secondary.

Demographic and clinical characteristics will not be stratified by a primary grouping variable.

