## 2. OBJECTIVES

The study includes patients with a diagnosis of AML who received Mylotarg (Gemtuzumab ozogamicin) in a real-world setting.

The study objectives are as follows. All analyses as described in Objectives 1 through 4 will be assessed across all patients using Mylotarg and will not be stratified by a grouping variable.

1. To describe the demographic and clinical characteristics as outlined in the variable list below for patients diagnosed with AML who received Mylotarg in a real-world setting.
  - a. Demographic characteristics will include age, race, body mass index (BMI), insurance status, and region of residence closest to the date of AML diagnosis.
  - b. Clinical characteristics will include comorbidity scores, Eastern Cooperative Oncology Group (ECOG) score, and disease characteristics such as stage at index date, cytogenetic testing results at index date, and de novo versus secondary AML diagnosis.
2. To describe the treatment patterns from the diagnosis of AML through the end of the third relapsed/refractory (R/R)-based line of therapy (R/R event, or disease progression, or death are considered as end events).

- a. Distribution of regimens within lines, for the first 3 R/R-based lines of systemic therapy.
  - b. Distribution of regimen sequences, across the first 3 R/R-based lines of systemic therapy.
  - c. Starting dose and dose changes of Mylotarg in each of the first 3 R/R-based lines of therapy.
  - d. Duration of Mylotarg treatment in each of the first 3 R/R-based line of therapy.
3. To describe the effectiveness outcomes of treatment of AML patients who received Mylotarg in a real-world setting.
    - a. Real-world event-free survival (rwEFS)/real-world relapse-free survival (rwRFS) in the first 3 R/R-based lines of therapy. The definition of rwEFS/rwRFS as described in [Section 4.3.2](#) is aligned to the extent possible using real-world data with that used by Pfizer in other studies.
    - b. Real-world overall survival (rwOS) from start of the initial line of therapy in which Mylotarg is used.
    - c. rwEFS/rwRFS/rwOS will be described across all patients.
  4. To evaluate response for each regimen in the first qualifying Mylotarg-containing R/R-based line of therapy among AML patients who received Mylotarg in a real-world setting.
    - a. First and best response, as outlined in [Section 4.3.6](#) will be described for each regimen in the first qualifying Mylotarg-containing R/R-based line of therapy.

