### 3.5.2. Derived Variables

Variables derived from abstracted and extracted data will include the following:

- Age at index date (Table 1).
- BMI at index date ( $\pm 30$  days) (Table 1).
- Geographic census region of patient's residence (Table 1).
- Weighted index of comorbid disease condition. Weighting of comorbid conditions will follow the weighting as specified in the Charlson Comorbidity Index (Table 2).
- Start and end dates and start and end dose of infused anti-cancer treatments from the index date through the end of the third R/R-based line of therapy or the end of the record, whichever occurs first.
- Dose changes of all oral (if applicable), infused, or injected anti-cancer therapies from the index date through the end of the first R/R-based line of therapy or the end of the record, whichever occurs first (Table 4).
- Start and end schedule of infused anti-cancer treatments from the index date through the end of the third R/R-based line of therapy or the end of the record, whichever occurs first (Table 3-Table 5).
- Treatment regimens, derived from oral and infused agents delivered, including start and stop dates, and indication of subsequent treatment after 1L (Table 3-Table 5).
- Duration of anti-cancer treatments regimens from the index date through the end of the third R/R-based line of therapy or the end of the record, whichever occurs first. Duration will be calculated as the end date of a regimen minus the start date of the corresponding regimen and will be computed during the analytics phase of the project (Table 5).
- Time under observation for analysis of rwEFS/rwRFS, by line, based on start date of treatment within line and dates of R/R event or disease progression, or censoring (Table 5-Table 7).
- Time under observation for analysis of rwOS from start of the first qualifying Mylotarg-containing R/R-based line of therapy, based on start of treatment in the first qualifying line setting, and based on date of death or censoring (Table 8).

- Time to best response for each regimen in the first qualifying Mylotarg-containing R/R-based line of therapy from the index date through the end of the third R/R-based line of therapy or the end of the record, whichever occurs first (Table 9-Table 11, Table 14-Table 15).

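### SAP 4.3.2 and Protocol 9.7.2 still start rwOS at first-line therapy, contradicting the Mylotarg origin used elsewhere; if programmed, this could only lengthen rwOS

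*SAP*

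**What the plan says.** The rwOS origin is stated in several places, and they do not agree.

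- **First-line origin.** SAP 4.3.2 gives it twice: "rwOS, from the first line of therapy through the end of record or death, whichever occurs first", and then "The time origin for analysis of rwOS is the start of therapy within the first line of therapy". Protocol 9.7.2 carries the same two statements. SAP 4.2 defines first line as starting with the first regimen after diagnosis, whether or not that regimen contains Mylotarg.
- **Start of the first Mylotarg-containing line.** Objective 3b in the SAP reads "Real-world overall survival (rwOS) from start of the initial line of therapy in which Mylotarg is used", and the protocol's matches. SAP 3.5.2 has "Time under observation for analysis of rwOS from start of the first qualifying Mylotarg-containing R/R-based line of therapy", as does Protocol 9.3.4 in substance. SAP 4.3.5 has "The time origin of rwOS analysis is the start of the earliest line of Mylotarg therapy", repeated in Protocol 9.7.5. The Table 8 title and footnote and the Figure 3 title follow this origin.
- **First Mylotarg use.** A later paragraph of SAP 4.3.5 starts rwOS at the first use of Mylotarg, which need not be the day its line began.

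Two cross-references matter. SAP 4.3.2 opens with "Single time to event analyses will be conducted as specified under the study objectives", which points to Objective 3b. SAP 4.3.5 says the time-to-event analysis described in 4.3.2 will be used, which points back to the first-line rule.

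For event-free survival (rwEFS), Protocol 9.7.2 says "rwEFS will be defined as the time from the treatment initiation date (for the first line of therapy) to the date of treatment failure". SAP 4.3.2 moved that origin to the treatment start "for the first agent in the first regimen in the first line of Mylotarg-containing therapy". It left rwOS and rwRFS on first line, although 4.3.5 starts rwRFS at Mylotarg.

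**The concern.** SAP 3.4.1 admits a patient only if Mylotarg was received within the first three lines. Nobody in the cohort can have died before receiving it. For a patient first treated with Mylotarg in line 2 or 3, the time from first-line start to Mylotarg is survival guaranteed by selection. A first-line clock counts that time as rwOS.

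SAP 4.1 lists rwOS among the primary endpoints. Two analysts, each following a sentence of the SAP, could report different medians from the same 20 to 30 patients. The study makes no comparison, so no treatment contrast is at risk. What is at risk is the absolute survival figure reported for Mylotarg-treated patients, and in a single-cohort descriptive study that figure is the result.

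**Working it through.** The documents give no expected rwOS, so there is no planned figure to reproduce. The check has four steps.

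**1. Direction.** For each patient let T be the time from Mylotarg to death and D the time from first-line start to Mylotarg, with D ≥ 0. The first-line clock records T + D, and the Mylotarg clock records T. Since T + D ≥ T for everyone, the first-line curve can never lie below the Mylotarg curve. The two agree only when D = 0 for all patients.

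**2. How long D can be.** SAP 3.4.1 accepts diagnoses from 1 December 2014. The protocol abstract places Mylotarg receipt on or after 1 September 2017. If that second date is a floor for Mylotarg receipt, the smallest possible D by first-line start date is as follows (30.4375 days per month):

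| First-line start | Days to 1 September 2017 | Months |
|---|---|---|
| 1 December 2014 | 1,005 | 33.0 |
| 1 January 2016 | 609 | 20.0 |
| 1 January 2017 | 243 | 8.0 |

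The first row is the boundary case, not a typical patient.

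**3. Illustrative cohort effect.** All inputs here are assumed: exponential survival after Mylotarg with median m, a share f first treated after line 1, a fixed delay d for that share, and no censoring. For t ≥ d,

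S(t) = 2^(−t/m) × [(1 − f) + f × 2^(d/m)],

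so the median is m × log2(2 × [(1 − f) + f × 2^(d/m)]) whenever this is at least d.

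For m = 12, f = 0.5, d = 6: the bracket is 0.5 + 0.5 × 1.414 = 1.207. The median is 12 × log2(2.414) = 15.3 months against 12.0, and 12-month survival is 0.5 × 1.207 = 0.60 against 0.50.

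First-line medians in months for d = 3 / 6 / 12:

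| f | True median 6 | True median 12 |
|---|---|---|
| 0 | 6.0 / 6.0 / 6.0 | 12.0 / 12.0 / 12.0 |
| 0.25 | 6.9 / 7.9 / 9.5 | 12.8 / 13.7 / 15.9 |
| 0.50 | 7.6 / 9.5 / 13.9 | 13.6 / 15.3 / 19.0 |
| 0.75 | 8.3 / 10.8 / 16.2 | 14.3 / 16.7 / 21.7 |

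In the cell m = 6, f = 0.25, d = 12 the median falls before d. It solves 0.75 × 2^(−t/6) + 0.25 = 0.5, giving t = 6 × log2(3) = 9.5.

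For scale, at m = 12 the simulated 95% sampling range of an uncensored median from Mylotarg is 6.2 to 21.1 months with 20 patients and 6.9 to 19.1 with 30. The mean upward shift at f = 0.5, d = 6 is about 3.3 months.

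The same formula sizes the gap between the two Mylotarg origins. If 10% to 50% of patients have a lag of 1 to 3 months from line start to first Mylotarg use, the median moves by 0.1 to 1.6 months for m = 6 or 12.

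**4. rwRFS.** SAP 4.2 separates refractory disease from relapse. On a first-line clock, a relapse before Mylotarg would end follow-up early, while a refractory first line would not count as a relapse and would add time. Assume a true median of 6.0 months from Mylotarg, half of patients treated after line 1, Mylotarg started at first-line failure, and exponential time to that failure with median 3, 6 or 12 months.

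- If all those failures were relapses, half the cohort has its event at first-line failure. The median solves 0.5 × 2^(−t/6) + 0.5 × 2^(−t/d) = 0.5, giving 4.2, 6.0 and 8.3 months. The same holds if any relapsed-or-refractory event counts, as another sentence of SAP 4.3.2 says.
- If all were refractory, that half contributes the sum of the two times. The median is 8.3, 9.9 and 12.0 months.

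The bias can go either way.

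**The case against.** The best reply is that the plan's intention is not in doubt. SAP 4.3.2 defers to the objectives, and Objective 3b names the Mylotarg line. The derived variable, the Objective 3 methods, Table 8 and Figure 3 agree with it, and no table shell exists for survival from first line. Protocol 9.7 lets the SAP modify the protocol's plans. On this view the first-line sentences are leftovers that a careful programmer would pass over. Most of that stands: the first-line origin is the outlier, and the partly updated rwEFS wording looks like an unfinished correction. It does not remove the problem. SAP 4.3.5 explicitly calls on 4.3.2, the SAP has no rule ranking one of its sections over another, and 4.3.5 itself gives two origins.

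Other limits also stand. The label primary comes from SAP 4.1 alone. The 33-month figure depends on how September 2017 is read: the second inclusion criterion in SAP 3.4.1 could attach that date to diagnosis, although the December 2014 date would then be redundant. Every cohort-level shift is assumed, and sampling error with 20 to 30 patients is often larger. The confidence interval in Table 8 conveys sampling error, however, and would not reveal a wrong origin.

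A reader might infer that reported rwOS will be inflated, or inflated by many months. The documents do not support that. It would take programming the outlier sentence over the objective, the methods and the table shell, and the size cannot be derived from what is given.

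**Conclusion.** The contradiction is real and should be removed before rwOS is programmed. The first-line rule conflicts with the objective it is meant to serve. If followed, it would lengthen rwOS for every patient first given Mylotarg after line 1 and shorten it for none. That direction needs only the eligibility rule. The size is unknown: zero if all patients began Mylotarg at the start of line 1, and 0.8 to 10.2 months on the median across the assumed non-zero shares and delays (12.8 − 12.0 to 16.2 − 6.0). The rwRFS wording has the same fault with no fixed direction.

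A reader might also infer that the line-start origin is unsound and that every objective, table and figure must move to first Mylotarg use. That goes too far. First use leaves no guaranteed time and line start usually leaves little, so the choice is minor provided it is made once.

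**What to change.** - In SAP 4.3.2, delete the first-line origin for rwOS and rwRFS. In Protocol 9.7.2, delete it for rwOS, rwEFS and rwRFS. Put one Mylotarg origin in its place.
- Make the two rwOS statements in SAP 4.3.5 agree on that origin, apply it to rwEFS and rwRFS for the first Mylotarg-containing line, and check it against Objective 3b and the footnotes of Tables 6 to 8. Keeping line start needs the fewest edits; choosing first use means aligning those places too.
- Keep the by-line rwEFS and rwRFS analyses of Objective 3a, labelled separately, each starting with its own line.
- Report how many patients first received Mylotarg in lines 1, 2 and 3.
- If survival from first-line start is also wanted, label it secondary and use delayed entry at first Mylotarg. Early risk sets may be small: only the share 1 − f is at risk at time zero, so 5 of 20 patients if f were 0.75 and 15 of 20 if it were 0.25.

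The cost is wording and at most one derived date, since treatment dates are already collected. Protocol 9.7 says major changes to primary endpoint definitions would be reflected in an amendment, so the sponsor should decide whether this correction counts as one.

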#### **9.7.5. Methods Under Objective 3**

*Objective 3: To describe the effectiveness outcomes of treatment of AML patients who received Mylotarg in a real-world setting.*

Analysis under this objective will include all study patients. The outcomes of interest under this objective are rwEFS/rwRFS and real world overall survival. Time to event analysis as described in [Section 9.7.2](#) will be utilized.

The Kaplan-Meier product limit estimator will be employed to evaluate rwEFS/rwRFS and rwOS. The time origin for these analyses will be the start of the treatment in the respective line of therapy for rwEFS/rwRFS for the first 3 R/R-based lines of therapy. The time origin of rwOS analysis is the start of the earliest line of Mylotarg therapy. rwEFS/RFS and rwOS analyses for lines of therapy will be limited to patients who received treatment during the line of interest.

The terminal event for analysis of rwEFS/rwRFS is the earlier of death or the first date of disease progression or R/R event following the time origin. Patients who have not died or experienced a disease progression or R/R event by the end of the medical record will be censored for analysis of rwEFS/rwRFS. The terminal event for analysis of rwOS is date of death. Note that Social Security Disability Insurance (SSDI) records have an expected lag of up to 4 months. Accordingly, patients who are not indicated to be deceased in clinical records or SSDI records will be censored for rwOS analysis as of the later of 1) the latest date known alive within the clinical record, 2) 4 months prior to the date of most recent SSDI update.

Separate Kaplan-Meier analyses will be conducted for each rwEFS/rwRFS and rwOS endpoint.

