### 3.4. Eligibility Criteria

#### 3.4.1. Inclusion Criteria

Patients must meet all of the following inclusion criteria to be eligible for inclusion in the study:

1. Confirmed diagnosis of AML on or after 01 December 2014 through Clinical Research Nurse (CRN) review of provider documentation of AML diagnosis in the medical record.
2. Receipt of Mylotarg at any point during first 3 R/R-based lines of therapy following initial AML diagnosis date occurring on or after 9/1/2017.
3. Age  $\geq 18$  years at initial diagnosis of AML.

There are no inclusion criteria related to minimum follow-up.

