A discontinuation will be defined as stopping of a particular agent for any reason, as indicated by provider documentation of “discontinuation” or “change in therapy” in the medical record, or, in the absence of provider documentation of discontinuation or change in treatment, a change in treatment with a particular agent, with no further treatment with that agent documented in structured data, or, evidence that the patient is admitted to hospice care (as the assumption is made that all systemic therapy is discontinued at that time).

For purposes of this study, first line therapy will be defined as beginning with the first regimen the patient receives after diagnosis of the disease of interest. Subsequent lines in this study will be defined as *R/R-based lines*. *R/R-based lines* are defined by the occurrence of an R/R event or a disease progression - either may be cited, in which an R/R event or disease progression must occur for a new regimen to be interpreted as a new line of therapy. In this study, **refractory** AML is defined as disease that is nonresponsive or failing to achieve at least minimal response while on therapy. **Relapsed** status is defined as the recurrence or worsening of disease following achievement of at least a minimal response. Additionally, the documentation of advancement of disease in patients after initial AML diagnosis but before initial AML treatment will be interpreted as a disease progression. R/R events and disease progression will be defined based on provider documentation, which primarily includes progress notes.

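### The SAP gives two incompatible populations and time origins for rwEFS/rwRFS; the by-line version puts patients without Mylotarg into the line-1 curve, selected on line-1 failure and survival

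*SAP*

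**What the plan says.** **By-line version.** SAP Objective 3a covers "real-world relapse-free survival (rwRFS) in the first 3 R/R-based lines of therapy". SAP 4.3.2 adds: "The time origin for analysis of rwEFS/rwRFS is the start of therapy within each specific line of therapy". SAP 3.5.2 derives the observation time for both endpoints by line, from the start of treatment in the line. SAP 4.3.5 opens with "Analysis under this objective will include all study patients. The outcomes of interest under this objective are rwEFS/rwRFS and rwOS", and its second paragraph sets the population: "rwEFS/rwRFS and rwOS analyses for lines of therapy will be limited to patients who received treatment during the line of interest". Protocol 9.7.5 matches this. Its time origin is the "start of the treatment in the respective line of therapy for rwEFS/rwRFS for the first 3 R/R-based lines of therapy", and its "analyses for lines of therapy will be limited to patients who received treatment during the line of interest".

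**First-Mylotarg-line version.** The later paragraphs of SAP 4.3.5 start both rwEFS and rwRFS at Mylotarg in the first line that uses it. Tables 6 and 7 and Figures 1 and 2 report only that analysis, in a single column. SAP 4.3.2 is itself mixed: its bullet starts rwEFS at the first Mylotarg-containing line but rwRFS at the first line of therapy.

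**Rules that interact with these.** Entry requires "Receipt of Mylotarg at any point during first 3 R/R-based lines of therapy", on or after 9/1/2017. On line changes, SAP 4.2 says that "an R/R event or disease progression must occur for a new regimen to be interpreted as a new line of therapy". SAP 4.1 names rwEFS/rwRFS among the primary endpoints.

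**The concern.** The by-line population asks for treatment in the line, not for Mylotarg in the line. A patient whose first Mylotarg is in line 2 is in the study only because line 1 ended in a relapsed/refractory event or progression and the patient lived to start line 2. Placing that patient in the line-1 curve conditions on the future. It also adds person-time without exposure to the drug under study. The same applies to lines 1 and 2 of a patient first treated in line 3. A line-2 curve would also include patients whose Mylotarg was in line 1 and who are now on something else.

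Two programmers could each follow the SAP faithfully and produce different primary-endpoint results. One of those results would describe neither outcome on Mylotarg nor outcome on the earlier therapy in an unselected group.

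**Working it through.** The documents give no figure to reproduce. N of 20 to 30 is a feasibility count and power is declared not applicable. The check is therefore the logic of the rules, followed by an illustration of size.

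**1. What the rules imply for a later-line user in the line-1 curve.** The answer depends on the event definition, and the documents contain three.
- *R/R event, progression or death* (Protocol 9.7.5; SAP 4.3.2 lists only R/R event or death). Reaching line 2 requires an R/R event or progression, so a line-1 event is certain, and death first or censoring in line 1 is impossible. Line 1 looks worse.
- *Relapse or death* (rwRFS in SAP 4.3.5). A patient refractory to line 1 has no relapse there and is certain to be alive until Mylotarg starts. That is guaranteed event-free time, so the bias can run upward.
- *Treatment failure, relapse from CR or better, or death* (rwEFS in SAP 4.3.5). Treatment failure is counted in Mylotarg cycles, so it cannot be assessed in a line without Mylotarg.

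**2. How many patients.** Count = N × s, where s is the share first given Mylotarg after line 1. The documents do not give s.
- s = 25%: 20 × 0.25 = 5 to 30 × 0.25 = 7.5, so about 5 to 8 patients.
- s = 50%: 10 to 15 patients.
- s = 75%: 15 to about 22 patients.

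**3. Event share.** If p is the line-1 event share among patients given Mylotarg in line 1, the mixed share under the first event definition is (1 − s)p + s. With p = 61% and s = 25%: 0.75 × 0.61 + 0.25 = 0.71. This exceeds p whenever p is below 100%.

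**4. Kaplan-Meier median (simulation; every input is an assumption except the dates taken from the documents).** Diagnosis is uniform from December 2014 to December 2019, with line 1 starting at diagnosis. Mylotarg is available from 1 September 2017, and records end about April 2020. Everyone has the same true line-1 event-time distribution. Of line-1 events, 30% are deaths, and line 2 starts one month after the event. The event is R/R event, progression or death. The 25% long-term share is prompted by the background statement that slightly more than 25% survive 3 or more years; that is survival, not event-free survival, so 0 and 40% are shown as well. Cells give the median in months (event share).

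| Long-term event-free | Median in the rest | Mylotarg in line 1 only | s = 25% | s = 50% | s = 75% |
|---|---|---|---|---|---|
| 0 | 6 | 6.0 (81%) | 6.0 (86%) | 6.0 (91%) | 6.0 (95%) |
| 0 | 10 | 10.0 (67%) | 9.9 (75%) | 9.7 (83%) | 9.6 (92%) |
| 25% | 6 | 9.5 (61%) | 8.3 (71%) | 7.4 (80%) | 6.6 (90%) |
| 25% | 10 | 15.9 (50%) | 13.3 (62%) | 11.7 (75%) | 10.5 (88%) |
| 40% | 6 | 15.3 (49%) | 10.5 (62%) | 8.4 (75%) | 7.0 (87%) |
| 40% | 10 | 26.2 (40%) | 16.8 (55%) | 13.2 (70%) | 11.0 (85%) |

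Falls in the median:
- No long-term share: 0.0 to 0.4 months.
- 25% share: 9.5 − 8.3 = 1.2 to 15.9 − 10.5 = 5.4 months.
- 40% share: 15.3 − 10.5 = 4.8 to 26.2 − 11.0 = 15.2 months.

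A repeat run agreed to within about 0.3 months.

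**5. Sensitivity to the 9/1/2017 rule.** A simpler model has a true exponential median of 10 months and 20/40/60% later-line users. Ignoring the date rule, the median reads 9.4/8.8/8.4 months; with the rule applied it reads 9.8/9.7/9.6. Leaving the rule out overstates the shift. The event share rises from 59% to 67/75/84%.

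**The case against.** The strongest reply is that the by-line sentences are leftovers. The paragraphs that follow them in SAP 4.3.5 define both endpoints from first Mylotarg, Tables 6 and 7 report only that, and no shell exists for rwEFS/rwRFS in line 1, 2 or 3. SAP 3.5.2 even points its by-line observation time to Tables 5 to 7. The objectives say that results will not be stratified by a grouping variable, no comparisons are planned, and N is only 20 to 30. With the origin at first Mylotarg, this selection does not arise.

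Most of that stands, and it limits the point. A reader might infer that the study's reported rwEFS/rwRFS will be biased, or that Objective 3a cannot be answered. The documents do not support either, because the only planned outputs use the first Mylotarg-containing line. A reader might also infer that every later-line user has a certain line-1 event on both endpoints. That holds only for the R/R event, progression or death definition.

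The reply does not remove the contradiction. The by-line rule is still stated in the objectives, the derived variables and both methods sections of the SAP, and in the protocol. Nothing says which text prevails.

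**Conclusion.** The point holds as an unresolved contradiction on the population and time origin of primary endpoints, with a selection bias if the by-line text is followed. The selection follows from the documents' own entry and line rules and needs no assumption. Its direction does not follow: it is downward under R/R event, progression or death, and possibly upward for rwRFS as relapse or death. For rwEFS, one component cannot be assessed at all in a line without Mylotarg.

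The effect on the median cannot be estimated from the documents. It runs from 0.1 months or less to several months, and further in the extreme scenarios, depending mainly on the unknown later-line share and on how many patients stay event-free long term. The rise in the line-1 event share appears in every scenario under the first event definition. The simulated figures assume no true difference between line-1 regimens; any real difference would come on top.

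**What to change.** - Make the definition in the later paragraphs of SAP 4.3.5 and Tables 6 and 7 the only one. Delete the by-line time origin and the sentence that admits anyone treated in the line.
- Align Objective 3a, SAP 3.5.2 and 4.3.2, and Protocol 9.7.2 and 9.7.5.
- In doing so, settle one detail. The SAP 4.3.5 text starts the clock at Mylotarg, whereas the table titles and footnotes start it at the line. These differ if Mylotarg enters in a later regimen of the same line, and starting at the line would then add guaranteed event-free time.
- If by-line results are wanted, limit each to patients whose first Mylotarg-containing line is that line, and add table shells.
- Show lines before the first Mylotarg only as treatment history in Table 3, with no survival curve.

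The cost is wording, with no new data. Protocol 9.7 says that major changes to primary endpoint definitions go into a protocol amendment, so one may be needed. Keeping by-line results means very small groups: at a 25% later-line share, about 5 to 8 patients across lines 2 and 3 together.
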